## 13.6 Special Situations

Uses of the IMPs outside what is foreseen in the protocol and defined below as "special situations" are subject to the same obligation to report as SAEs. All special reporting situations, even in absence of an AE, that occur during the defined study period must be recorded on the source documentation, in the eCRF and reported to the sponsor using the SAE report form without undue delay but not later than within 24 hours after awareness by anyone of the study team members at the site.

#### Pregnancy / Breast feeding / Lactation exposure

For more details refer to see section 13.5.

#### Overdose

An overdose, accidental or intentional, whether or not it is associated with an AE, or abuse, withdrawal, sensitivity or toxicity to an investigational product should be reported on the SAE form / event of special reporting situations form. If an overdose is associated with an AE, the overdose and adverse event should be reported as separate terms.

#### Abuse

Intentional, non-therapeutic use of a drug product or substance, even once, to achieve a desired psychological or physiological effect. Therefore, abuse potential refers to the likelihood that abuse will occur with a particular drug product or substance with CNS activity. Desired psychological effects can include euphoria, hallucinations and other perceptual distortions, alterations in cognition, and changes in mood.

#### Misuse

Any intentional therapeutic use of a drug product in an inappropriate way. Inappropriate use should be considered in the context of the clinical study protocol.

#### Transmission of infectious agents

Suspected transmission of an infectious agent by a medicinal product will be reported on the SAE report form.

#### Medication Error

An unintended failure in the drug treatment process. Examples include administration of a drug product in the wrong dose, by an incorrect route, or to the wrong person; administration of a drug product resulting in a drug interaction due to drugs or foods that are known to interact; administration of the wrong drug product; or inadvertently consuming a greater than prescribed dose of a drug product (e.g. double dose) due to memory lapse. Therapeutic errors may be made by the patient, physician, pharmacist, clinical study staff etc.

#### Inadvertent or accidental exposure

Exposure to an IMP, as a result of one's professional or non-professional occupation.

#### Unexpected therapeutic benefit or clinical benefit

To explore potential new indications for the study drug, any unexpected therapeutic benefits not associated with WM (e.g. unexpected hair growth is stimulated by one of the study drugs).

#### 13.7 Reporting of Serious Adverse Events

All events that meet one or more criteria of seriousness that occurred from the time of patient's first application / intake of IMPs up to 30 days after the last study drug intake, regardless the relationship to the study drugs require the completion of a SAE report form in addition to being recorded on the AE page of the eCRF.

A SAE that occurs after this time, if considered related to the study drugs, will be reported regardless of the time between the last drug administration and the event onset.

The investigator shall report serious adverse events to the sponsor / ZKS Ulm without undue delay but not later than within 24 hours of obtaining knowledge by e-mail, using the SAE report form. Where relevant, the investigator shall send a follow-up report to the sponsor (with the same time requirements) to allow the sponsor to assess whether the serious adverse event has an impact on the benefit-risk balance of the clinical trial.

The investigator is required to ensure that the data on these forms is accurate and consistent. This requirement applies to all SAEs (regardless of relationship to study drugs) that occur during reporting period, and those made known to the investigator at any time thereafter that are considered being related to study drugs.

All serious adverse events that have not resolved by the end of the study, or that have not resolved upon discontinuation of the patient's participation in the study, must be followed until any of the following occurs:

- the event resolves;
- the event stabilizes;
- the event returns to baseline, if a baseline value / status is available;
- the event can be attributed to agents other than the study drug or to factors unrelated to study conduct;
- it becomes unlikely that any additional information can be obtained (patient or health care practitioner refusal to provide additional information, lost to follow-up after demonstration of due diligence with follow-up efforts).

## 13.7.1 Obligations of the investigator

In case of SAE, special situation or pregnancy, the investigator shall report them to the sponsor / ZKS UIm without undue delay but not later than within 24 hours of obtaining knowledge by e-mail to:

## [contact]

# All SAE forms must be dated and signed by the responsible investigator or one of his / her authorized medical staff members.

- The SAE report should provide a detailed description of the SAE specifying the date of onset, severity, duration, relevant concomitant medication, relevant medical history, relevant lab data, action taken regarding study medication, corrective therapy given, outcome of all serious adverse events and the investigator's opinion as to whether the serious adverse event can be related to the study drugs. Whenever possible, symptoms should be grouped as a single syndrome or diagnosis.
- All information for detailed description of the SAE may not be available at the time of the initial report. Nevertheless, initial reports should be submitted as long as at least the following minimum criteria are met:
  - o an identifiable patient;
  - a suspected medicinal product;
  - o an identifiable reporting source;
  - an event that can be identified as serious;
  - a causality assessment (if investigator causality assessment is not provided, the worst case scenario is assumed and the event will be considered related).
- Information about results of any examinations carried out including laboratory tests that are important for the diagnosis, assessment, or treatment of a SAE and the dates on which these examinations were performed should be given within the SAE form. For laboratory tests the units and the respective normal reference range should be provided as well.
- Additional information to any SAE should be actively sought and reported by the investigator / site on a subsequent SAE report follow up form and sent by e-mail to the sponsor / ZKS Ulm as soon as they become available. Missing information to any SAE that is fatal or life threatening should be provided as soon as possible, but not later than within 3 further calendar days. If a patient died and an autopsy has been performed, copies of the autopsy report and death certificate are to be sent as soon as these become available. A translation of the autopsy report and death certificate into English language has to be provided, if written in a language other than English or German.
- Where required by local legislation, the investigator is responsible for informing the EC of the SAE and providing them with all relevant initial and follow-up information about the event. The investigator / site must keep copies of all SAE information on file including correspondence with the sponsor / ZKS UIm and the EC.

#### 13.7.2 Safety Queries

Queries pertaining to SAEs will be communicated from the sponsor / ZKS Ulm to the site by email. The response time is expected to be no more than 24 hours for urgent queries (e.g. fatal or life-threatening SAEs, missing causality assessment) and for all other queries 5 calendar days.

#### 13.7.3 Obligations of the sponsor

The expectedness of an adverse reaction will be determined by the sponsor according to the RSI of the IMPs.

Expedited reporting (SUSAR, New Safety Issues), and submission of Development safety update reports to the relevant CA and to the EC, as appropriate, in accordance with current legislation will be performed by the sponsor / ZKS Ulm.

During the course of the study, the sponsor will report in a pseudonymized, expedited manner all SAEs that are both unexpected and suspected to be related to study drugs, by either the investigator or the sponsor, to the EudraVigilance database, concerned EC and to the investigators in each country / site in accordance with international and local regulations:

- within 7 calendar days of first knowledge by the sponsor for fatal or life-threatening events. Relevant missing information for fatal- or life-threatening cases will be subsequently submitted within an additional 8 calendar days.
- within 15 calendar days of first knowledge by the sponsor for all other serious adverse events.
- All FU reports will be submitted within 15 calendar days of knowledge by the sponsor.

Once the trial is transitioned to CTIS SUSARs will only be reported to the EudraVigilance database in compliance with regulatory timelines; the investigators will be informed by periodic SUSAR Line Listing twice per year together with a summary analysis of safety profile and updated benefit risk for the ongoing clinical trial. Single SUSAR CIOMS I reports will only be distributed to the investigators if the safety of the participants is adversely affected. In addition after the transition the annual safety report will be uploaded to CTIS.

## 13.8 Product quality complaint handling

A product quality complaint (PQC) is defined as any suspicion of a product defect related to manufacturing, labeling, or packaging, i.e. any dissatisfaction relative to the identity, quality, durability, or reliability of a product, including its labeling or package integrity (e.g. damaged or broken product, packaging issues, issues with product appearance, missing component / product). A PQC may have an impact on the safety and efficacy of the product. Timely, accurate, and complete reporting and analysis of PQC information from studies are crucial for the protection of patients, investigators, and the sponsor, and are mandated by regulatory authorities worldwide.

All initial PQCs of an IMP must be reported to sponsor and supporting companies by the studysite personnel within 24 hours after being made aware of the event. If the defect is combined with a SAE, the investigational staff must report the PQC to sponsor / ZKS Ulm according to the SAE reporting timelines. A sample of the suspected product if possible should be maintained for further investigation.

## 13.9 Protocol Deviations and Serious Breach

## **13.9.1 Protocol Deviations**

Protocol deviations are documented by the site staff for each center in a special area in the eCRF. The CRA supports the center if necessary and escalates to the sponsor if necessary. The sponsor assessment takes place at regular intervals. The sponsor takes appropriate measures to ensure patient safety and data quality.

## 13.9.2 Serious Breach

The following section will become applicable only after this protocol has been approved by authorities after transition to the EU regulation 536/2014. The study centers will be adequately informed by the sponsor.

A serious breach is any deviation of the approved protocol version or the clinical trial regulation that is likely to affect the safety of a trial participant and/or the rights of trial participants and/or data reliability and robustness to a significant degree in a clinical trial.

Suspected serious breaches, as well as any communication related to the suspected serious breach have to be reported to the sponsor / ZKS Ulm and CTO by e-mail using the following email-address: [contact] within 24h of knowledge. The sponsor provides a "Serious Breach Report Form" to support the completeness of the documentation. Queries pertaining to suspected serious breaches will be communicated from the sponsor / ZKS Ulm or CTO to the reporter by e-mail (urgent query is indicated in the subject header of the email). The response time for any query is expected to be no more than 24 hours.

The sponsor will assess each suspected serious breach to decide whether it should be reported as a serious breach.

CTO will notify (upload of the final document in the EU portal) any serious breach according to the EU Regulation 536/2014 without undue delay and at the latest within 7 calendar days of the sponsor becoming aware of a serious breach. Participating centers, including participating pharmacists, as well as clinical research associates (CRAs) and other designees of the sponsor, will support the sponsor by promptly reporting suspected serious breaches.

# 14. STATISTICAL CONSIDERATIONS

The primary goal of this study is to explore the efficacy of Carfilzomib in combination with lbrutinib compared to lbrutinib alone in the treatment of WM.

### 14.1 Endpoints

Following endpoints will be considered in this study:

#### 14.1.1 Primary Endpoint

The primary endpoint is the rate of CR / VGPR 12 months after randomization.

#### 14.1.2 Secondary Endpoints

The following secondary efficacy endpoints will be evaluated:

#### Response rate

The response rates (CR, VGPR, PR, MR) and ORR (CR, VGPR, PR) are evaluated 12 and 24 months after randomization.

#### Best response

Best response (at least achieving a MR) is determined in the time interval from randomization to end of follow-up.

#### Time to best response

Time to best response is defined as the time from randomization to best response the patient achieves (CR, VGPR, PR, MR).

#### Time to first response

Time to first response is defined as the time from randomization to first response (MR, PR, VGPR or CR).

#### Time to treatment failure (TTF)

TTF is defined as the time from date of randomization to discontinuation of therapy for any reason including death from any cause, progression, non-tolerable toxicity or add-on of new anti-cancer therapy. Patients alive without progression and relapse or other treatment failure will be censored at the latest tumor assessment date.

#### Response duration (RD)

Response duration will be calculated in patients with response (CR, VGPR, PR, MR) from the date of response to the date of progression, relapse or death from any cause. Patients alive without progression and relapse will be censored at the latest tumor assessment date.

#### Progression Free Survival (PFS)

PFS will be calculated from the date of randomization to the following events: the date of progression (as defined in appendix 21.1) and the date of death if it occurred earlier. Patients alive without progression and relapse will be censored at the latest tumor assessment date.

#### Cause specific survival (CSS)

Cause specific survival is defined as the period from the randomization to death from lymphoma or lymphoma related cause (e.g. infections, bleeding, amyloid caused organ failure); death unrelated to WM is considered as a competing event.

### Overall survival (OS)

Overall survival is defined as the period from the randomization to death from any cause. Patients who have not died until the time of the analysis will be censored at their last contact date.

#### Safety

Safety including adverse events, SAEs, laboratory parameters, ECG and vital signs.

## Quality of Life

Quality of Life will be assessed by the FACT-Lym questionnaire as indicated in Table 1, Table 2 and Table 3.

## 14.2 Sample size estimation

## RCT - arms A and B:

The sample size calculation is based on the comparison of the primary endpoint (CR / VGPR rate) between the arms A and B using the one-sided chi-square test. According to Treon et al. (NEJM 2015) the CR / VGPR rate in WM patients treated with Ibrutinib is about 16%. We see an increase from 16% to 35% CR / VGPR as a clinically relevant increase, which corresponds to a more than doubling of deep remissions. Deep remissions correlate with PFS and the disease-free interval, thus we assume that the risk-benefit ratio justifies the addition of Carfilzomib when we achieve this improvement. Assuming a CR / VGPR rate of 35% in patients treated with Carfilzomib and Ibrutinib, this scenario requires a number of 94 patients (i.e. 47 patients per group) to reach a power of 80% at a one-sided type one error of 0.10. It is expected that the rate of withdrawal in the study is smaller than 5%. In addition to the drop-out rate of 5%, patients who were randomized but withdrew consent before the start of therapy may be replaced until the end of the recruitment period. According to this, the study will enroll approximately 99 patients in the arms A and B in total.

## 14.3 Statistical analysis

The primary study endpoint CR / VGPR rate will be evaluated following the intention to treat principle. The chi square test will be used for the analysis of the primary endpoint to test the CR / VGPR rate in the arms A and B at the 10% significance level (one-sided) in the core analysis population. The corresponding set of null and alternative hypothesis is:

H0: RRA  $\leq$  RRB

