## 12.5 Randomization Procedure

A stratified central block randomization will be used to allocate the patients 1:1 to the 2 arms. Stratification factors are MYD88 and CXCR4 status with the following groups: MYD88mut/CXCR4non-mut; MYD88mut/CXCR4mut; MYD88non-mut/CXCR4non-mut (MYD88non-mut/CXCR4mut not applicable) and number of prior lines (0 vs.  $\geq$  1 treatment lines). A stratification by site is not feasibly due to the rare disease status and the high number of sites (approximately 30 sites).

In this study an electronic randomization will be used. For electronic randomization each site will log on to the eCRF (only authorized personal). The questions for stratification factors and questions on inclusion / exclusion criteria have to be answered prior to randomization. The treatment arm assigned to the patient will be shown immediately and sent by e-mail to site personnel and sponsor in addition. A user manual describing the randomization and documentation process will be distributed to each site.

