### HA: RRA > RRB

where RRA is the CR / VGPR rate in arm A (Carfilzomib / Ibrutinib) and RRB is the CR / VGPR rate in arm B (Ibrutinib). If the obtained one-sided p-value is less than or equal to 0.1 and the point estimate for the CR / VGPR rate of arm A is larger than that of arm B, it will be concluded that the Carfilzomib / Ibrutinib combination statistically significantly increases CR / VGPR rate compared to single agent Ibrutinib. Additionally, the two-sided 95% confidence interval (CI) of the rate difference (RRA-RRB) will be calculated as effect estimator. Further exploratory analyses of the primary study endpoint encompass the Cochran-Mantel-Haenszel (CMH) test of rate difference adjusting for stratification factors (MYD88 and CXCR4 status and number of prior lines). A CMH 95% stratified confidence interval (CI) of the rate difference (RRA-RRB) with each rate weighted by the number of patients in each stratification factor combination will be calculated as an effect estimator. Additionally, logistic regression models will be used to investigate the influence of putative risk factors on the CR / VGPR rate.

All secondary endpoints will be analyzed exploratory. Group comparisons in binary endpoints will be performed two-sided using the chi square test or Fisher's exact test as appropriate. Additionally, 95% CIs will be calculated for group differences. Survival times will be analyzed using the Kaplan-Meier estimator incl. 95% CI. Furthermore, the Cox Proportional Hazard model will be used to investigate the influence of putative risk factors on survival time. Group comparison in quality of life (ordinal endpoint) will be performed using the Wilcoxon rank-sum test. Additionally, the 95% CI will be calculated for the difference of the medians.

For safety analysis of the RCT, all adverse events will be listed and the frequencies of the most frequent will be calculated. Group comparisons (A vs. B) of frequencies of AEs and SAEs will be performed using the chi square test or Fishers exact test as appropriate.

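### The primary test is an unstratified chi-square although randomisation is stratified by genotype and prior lines; making the already planned stratified CMH test primary is a small improvement at no cost

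*Protocol*

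**What the plan says.** **Randomisation (section 12.5).** "A stratified central block randomization will be used to allocate the patients 1:1 to the 2 arms". The factors are MYD88/CXCR4 status in three groups and prior lines in two (0 versus at least 1), so there are six cells.

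**Why genotype matters (section 7.6.1).** The protocol says that ibrutinib's activity depends on genotype. It gives major response rates (at least PR) of 91.7%, 61.9% and 0% for MYD88-mutated/CXCR4 wild-type, MYD88-mutated/CXCR4-mutated and double wild-type patients.

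**Primary test (section 14.3).** "The chi square test will be used for the analysis of the primary endpoint", one-sided at the 10% level. Success requires p of at most 0.10 and a higher point estimate in arm A.

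**Stratified analysis (section 14.3).** "Further exploratory analyses of the primary study endpoint encompass the Cochran-Mantel-Haenszel (CMH) test of rate difference adjusting for stratification factors". A stratified 95% interval labelled CMH is also planned, "with each rate weighted by the number of patients in each stratification factor combination".

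**Unstratified interval (section 14.3).** "Additionally, the two-sided 95% confidence interval (CI) of the rate difference (RRA-RRB) will be calculated as effect estimator".

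**Sample size (section 14.2).** It rests on the same one-sided chi-square: 47 per arm, 94 in total, about 99 enrolled.

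**The concern.** The trial balances allocation on factors that it regards as prognostic, then leaves them out of the test that decides the result. Balancing within strata removes between-stratum variation from the true sampling variance of the rate difference. The pooled chi-square still counts that variation. If the strata are prognostic for CR/VGPR, the test is therefore slightly conservative and gives up some power that the stratification has already bought. A test that uses the strata is already in the plan.

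The second concern is the stratified interval. Weighting each rate by the number of patients in the stratum is not Mantel-Haenszel weighting. If a small stratum has patients in one arm only, it keeps a positive weight while the rate in its empty arm is 0/0, so the estimate does not exist as described.

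**Working it through.** **1. The plan's own figure.** Inputs from section 14.2: "the CR / VGPR rate in WM patients treated with Ibrutinib is about 16" per cent; "Assuming a CR / VGPR rate of 35% in patients treated with Carfilzomib and Ibrutinib"; and "to reach a power of 80% at a one-sided type one error of 0.10".

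With pooled rate (0.16 + 0.35)/2 = 0.255:

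n per arm = [1.2816·√(2·0.255·0.745) + 0.8416·√(0.16·0.84 + 0.35·0.65)]² / 0.19² = (0.790 + 0.506)² / 0.0361 ≈ 46.5, so 47.

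Total 94; 94/0.95 = 98.9, so 99. Power at 47 per arm is 0.803 by formula and 0.812 by exact enumeration. The stated size reproduces, and it belongs to the chi-square that the plan uses.

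**2. Chi-square against CMH.** Both reject at z ≥ 1.2816. The CMH statistic over strata k, with t the responders in the stratum, is

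z = Σ(x_A − n_A·t/n) / √Σ[n_A·n_B·t·(n − t) / (n²(n − 1))].

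Inputs taken from the protocol:
- MYD88-unmutated share 13% (section 7.2 gives 87% mutated).
- Treatment-naive share 45% (from the ibrutinib/rituximab phase III trial described in section 7.4).

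Inputs assumed, because the protocol does not give them:
- CXCR4-mutated share 35% of MYD88-mutated patients, and blocks of 4.
- Stratum-specific CR/VGPR rates. Arm B rates by genotype (unmutated last) were 0.205/0.123/0.051 (mild) or 0.255/0.051/0 (strong), averaging 0.16 overall. Arm A was either 19 points higher in every stratum or higher by the ratio 0.35/0.16.

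Results with 99 patients and 6,000 runs (Monte Carlo standard error about 0.5 points for power and 0.4 for type I error):

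| Strata | Effect | Power, chi-square | Power, CMH | Type I error, chi-square | Type I error, CMH |
|---|---|---|---|---|---|
| Equal rates | – | 0.828 | 0.826 | 0.104 | 0.103 |
| Mild | difference | 0.829 | 0.827 | 0.108 | 0.110 |
| Mild | ratio | 0.825 | 0.835 | as above | as above |
| Strong | difference | 0.829 | 0.838 | 0.096 | 0.105 |
| Strong | ratio | 0.840 | 0.871 | as above | as above |

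Simulations at other sizes agree:
- 96 patients: power 0.82 against 0.81–0.82 with equal rates, and 0.83–0.84 against 0.85–0.86 with strong strata. Chi-square type I error with strong strata was 0.085–0.087.
- 94 patients, 7% unmutated: 81.4% against 80.8% with weak strata, and 85.9% against 87.0% with strong strata. Chi-square type I error with prognostic strata was 0.088–0.096.

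**3. Check of the conservatism by hand.** Under the null with strong strata, the stratum shares are 0.87·0.65 = 0.5655, 0.87·0.35 = 0.3045 and 0.13. The pooled variance term is 0.16·0.84 = 0.1344. The within-stratum term is 0.5655·0.255·0.745 + 0.3045·0.051·0.949 + 0 = 0.1222. The effective cut-off is 1.2816/√(0.1222/0.1344) = 1.344, an upper tail of about 0.089. The simulated 0.085–0.096 scatters around this. With mild strata the within-stratum term is 0.1313, the cut-off 1.297 and the tail about 0.097.

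**4. Strata with one empty arm.** The smaller MYD88-unmutated cell has expected size 99·0.13·0.45 = 5.8 patients, or 99·0.05·0.45 = 2.2 if only 5% are unmutated. Simulated probability of at least one occupied stratum with a single arm:

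| MYD88-unmutated share | Probability | Conditions |
|---|---|---|
| 13% | about 5% (3–7%) | 99 patients, blocks of 2–6, 0–5% missing |
| 10% | 8–19% | same |
| 7% | 33–35% | 94–96 patients, blocks of 4 |
| 5% | 38–58%; 51–55% with blocks of 4 | 94–99 patients |

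For a stratum with n_A = 2 and n_B = 0, the stratum-size weight is 2 while the arm B rate is 0/0. The Mantel-Haenszel weight is 2·0/2 = 0, and the estimate stays defined.

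**The case against.** The strongest defence is that nothing here is wrong. The test and the sample size agree, type I error stays near or below nominal, power stays above 80% in every scenario, and section 14.3 already plans a CMH test, a stratified interval and logistic regression. The gain needs strata that are prognostic for CR/VGPR, whereas the genotype figures in section 7.6.1 are for major response. With flat strata the CMH test is level or up to about one point worse. All of this stands, and it is why the point is an improvement and not a correction.

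On the interval, the wording may be a loose description of Mantel-Haenszel weights, which are themselves built from stratum counts, and the formula may be set out in the SAP. If so, the difficulty disappears. The estimate is in any case exploratory and outside the decision rule. What remains is that the protocol's sentence, read as written, describes different weights and should be corrected.

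A reader might also infer that the 95% interval conflicts with the one-sided 10% test. At 47 per arm and 16% versus 35%, exact enumeration gives a probability of 0.225 (0.225/0.812 = 28% of positive trials) that the test rejects while a 95% Wald interval includes zero. For example, 12/47 versus 7/47 gives z = 1.284 with a lower limit of -5.5 points. This follows from one-sided 0.10 being looser than one-sided 0.025. The decision rule uses the p-value, and the protocol offers the interval as an effect estimate, so it is not an error.

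**Conclusion.** The point holds as an efficiency and alignment matter. Moving the decision to the stratified CMH test changes power by about -1 to +3 points. With strongly prognostic strata it also brings type I error from about 0.09 (0.085–0.096 across simulations) closer to 0.10. The size depends on assumed stratum-specific CR/VGPR rates, CXCR4 share and block size. The planned 94/99 need not change.

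Three stronger readings are not supported:
- That the unstratified test is invalid or contradicts the design. It is valid and matches the sample size.
- That the weights of the stratified interval are undefined. Stratum counts are always known; only the weighted difference fails when an arm is empty.
- That an empty arm is to be expected. On the protocol's own 87% MYD88-mutated figure it occurs in about 5% of trials. It becomes common only if the unmutated share is well below 13%, which is possible because that figure comes from a study of 30 samples.

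**What to change.** In section 14.3 and the synopsis:

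- Make the one-sided CMH test, stratified by the six randomisation cells and without continuity correction, the primary test at 0.10. Keep the unstratified chi-square as a sensitivity analysis. If the sponsor prefers the present order, give the reason.
- State the weights of the stratified rate difference as n_A·n_B/(n_A + n_B), so that a stratum with one empty arm gets weight zero, and name a matching variance such as Sato's.
- Optionally, report a two-sided 80% interval, which corresponds to the test, next to the 95% interval. This is presentation only.

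The cost is wording. Both tests are already planned, and no patients, data or change in sample size are needed. The change should be made before outcomes are compared by arm.
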